11.3.5. Pregnancies: Reporting and Follow-up of Subjects

A pregnancy in a female subject or a male subject's female partner must be confirmed by a positive serum beta-hCG test. If a female subject or the female partner of a male subject becomes pregnant while the subject is receiving study treatment or within 3 months after the last dose of study treatment, a Pregnancy Report Form must be completed and submitted to FibroGen within 24 hours of the investigator learning of the pregnancy. A pregnant subject is immediately withdrawn from receiving study treatment. The investigator must follow the pregnancy to completion to ascertain both its outcome and whether any AEs occur.

Pregnancy itself is not an AE. Abortion, whether accidental, therapeutic, or spontaneous, should always be classified as serious, recorded on an SAE Report Form, and reported to FibroGen within 24 hours of the investigator learning of the event. Similarly, any medically significant congenital anomaly/birth defect in a child born to a female subject or the female partner of a male subject exposed to the investigational product should be recorded and reported as an SAE.

The outcome of the pregnancy must be reported by the investigator on a Pregnancy Outcome Report Form, which should be sent to FibroGen within 24 hours of the investigator learning of the outcome.

11.3.6. Abnormal Laboratory Findings

Laboratory values will be collected throughout the study to assess for safety. The investigator must review and assess all laboratory results in a timely manner and must report abnormal laboratory findings if they are clinically significant or if there are associated signs and symptoms.

An abnormal laboratory finding in absence of any other signs or symptoms is not necessarily an AE/SAE. If the abnormal laboratory finding is accompanied by signs or symptoms, report the signs and symptoms as the AE/SAE in lieu of the abnormal laboratory value. If a diagnosis is available, report the diagnosis.

Clinically significant laboratory abnormalities that reflect a change from the initial screening value and that require active management may be considered AEs (e.g., abnormalities that require study treatment dose modification, discontinuation, more frequent follow-up assessments, etc.). However, out-of-range Hb values should not be reported as AEs as these Hb values will be captured and analyzed in the efficacy analyses.

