4.5.1. Hepatic Safety Monitoring

The guidelines described in this section are intended to enable early detection and action following abnormal liver function test (LFT) results. **It is the responsibility of the Investigator to expeditiously review LFTs, follow these guidelines and contact the Medical Monitor if a study subject meets any of the LFT abnormalities specified below.** In addition, repeat LFTs 2 to 3 times weekly, then weekly or less until abnormalities stabilize or return to within normal limits. LFTs should include the usual 4: ALT, AST, Tbili and ALP

Table 1: Summary of investigator actions with respect to Hepatic Monitoring

Repeat LFTs within 2 to 3 days if:	Discontinue Study Drug if:

 ALT or AST > 3 x ULN, or Tbili > 2 x ULN 	
 ALT or AST > 8 x ULN, or ALT or AST > 5 x ULN for > 2 weeks, or ALT or AST > 3 x ULN and (Tbili > 2 x ULN or INR > 1.5), or ALT or AST > 3 x ULN with appearance of fatigue, nausea, vomiting, right upper quadrant pain or tenderness, fever, rash, and/or eosinophilia (> 5%)

Abbreviations: ALP = alkaline phosphatase; ALT = alanine aminotransferase; AST = aspartate aminotransferase; GGT = gamma-glutamyl transferase; INR = international normalized ratio; LFT = liver function test; Tbili = total bilirubin; ULN = upper limit of normal.

If close monitoring for LFTs in a subject is not possible, study drug should be discontinued. Evaluate the subject for potential causes, which may include the following:

- Detailed history of symptoms and prior or concurrent diseases
- Concomitant drug use, including nonprescription medications, herbal and dietary supplements, alcohol or recreational drug use, or special diets
- Exposure to environmental chemical agents

- Rule out acute viral hepatitis Types A, B, C, D, E; autoimmune or alcoholic hepatitis; nonalcoholic steatohepatitis; hypoxic/ischemic hepatopathy; biliary tract disease
- Obtain additional tests as appropriate: eg, INR, GGT or direct bilirubin; ultrasound or other imaging to assess biliary tract disease
- Consider gastroenterology or hepatology consultations

Once LFTs return to normal, and depending on whether there is an explanation for the LFT elevations, study drug dosing may resume, after discussion with the Medical Monitor

Ref: FDA Guidance for Industry, titled: "Drug-Induced Liver Injury: Premarketing Clinical Evaluations", issued July 2009

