11 SAFETY ANALYSES

11.1 ADVERSE EVENTS

An AE (classified by preferred term) occurring after the first dose of study medication and up to the last dose of study medication +28 days is considered a treatment emergent adverse event (TEAE) if it was not present prior to the first dose of study medication, or it was present prior to the first dose of study medication but increased in severity during the treatment period.

The number and percentage of subjects reporting TEAEs are tabulated by system organ class and preferred term. If more than one event occurs with the same preferred term for the same patient, the patient is counted only once for that preferred term using the most severe and most relatedness occurrence for the summarization by severity and by relationship to the study medication. In addition to the frequency tables above, crude event rate are provided. The crude event rate of interest (per 100 patient exposure years) by system organ class and preferred term is calculated as: number of the events per PT and SOC / total patient exposure years (PEY)*100.

The following TEAE table and listings are provided.

1. TEAE by system organ class and preferred term
2. TEAE by system organ class, preferred term, and maximum severity
3. TEAE by system organ class, preferred term, and relationship to study medication
4. Treatment-emergent serious AEs (TESAE) by system organ class and preferred term
5. TEAEs leading to discontinuation of study medication or from the study will be summarized by preferred term and treatment group
6. Listing of subjects with serious adverse events (SAEs)
7. Listing of subjects with adverse events leading to discontinuation of study medication or from the study

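### Protocol 11.3.6 contradicts itself on symptomatic laboratory findings, so an undiagnosed symptomatic liver-enzyme rise that meets Table 1 may reach the AE tables under a symptom term only

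*Protocol*

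**What the plan says.** Protocol 11.3.6 (Abnormal Laboratory Findings) addresses the point in three consecutive paragraphs.

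- First paragraph: the investigator "must report abnormal laboratory findings if they are clinically significant or if there are associated signs and symptoms".
- Second paragraph: "An abnormal laboratory finding in absence of any other signs or symptoms is not necessarily an AE/SAE". Where symptoms are present, the site is to "report the signs and symptoms as the AE/SAE in lieu of the abnormal laboratory value". The next sentence adds: "If a diagnosis is available, report the diagnosis".
- Third paragraph: "Clinically significant laboratory abnormalities that reflect a change from the initial screening value and that require active management may be considered AEs". The examples given are "abnormalities that require study treatment dose modification, discontinuation, more frequent follow-up assessments, etc".

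Protocol 4.5.1, Table 1, lists four criteria for discontinuing study drug. One of them is "ALT or AST > 3 x ULN with appearance of fatigue, nausea, vomiting, right upper quadrant pain or tenderness", with fever, rash and eosinophilia also on the list.

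SAP 11.1 tabulates TEAEs by system organ class and preferred term. It also states: "TEAEs leading to discontinuation of study medication or from the study will be summarized by preferred term and treatment group". The SAP text specifies no hepatic grouping of terms.

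**The concern.** The combination of raised transaminases and symptoms is one that Table 1 treats as serious enough to stop drug. It is also the combination for which the second paragraph of 11.3.6 has the symptom replace the laboratory value. A site that follows that sentence, with no diagnosis in hand, records the symptom alone. Because the SAP tables are built on preferred terms, they carry that symptom term forward, and a stop made under a liver criterion can be shown as a stop for nausea or fatigue.

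Long-term safety is part of the primary objective, and the liver has its own monitoring plan in this protocol. Causality may be affected too. Protocol 1.2 names fatigue as a consequence of anemia, and 11.3.3 classes events that represent the underlying disease as not related. A liver episode recorded as fatigue could fall into that category more easily than one recorded under a hepatic term.

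**Working it through.** The documents give no figure to reproduce. The check is a reading of 11.3.6 against Table 1 and the SAP, followed by a small illustration of scale.

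**Step 1. Apply 11.3.6 to a subject with ALT or AST above 3 x ULN plus a Table 1 symptom.**

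| Situation | Governing text in 11.3.6 | Term reaching the AE tables |
|---|---|---|
| Diagnosis available | Second paragraph, diagnosis sentence (directive) | The diagnosis; hepatic if the diagnosis is hepatic |
| No diagnosis, investigator uses the active-management clause | Third paragraph (permissive) | A laboratory term is possible |
| No diagnosis, investigator follows the substitution sentence literally | Second paragraph (directive) | Symptom only |

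The first paragraph's requirement to report the finding points away from the third row, but the substitution sentence points to it. Nothing in the section says which prevails. Of the two clauses that bear on the undiagnosed case after the first paragraph, the one that drops the laboratory term is an instruction and the one that keeps it is an option.

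**Step 2. How much of Table 1 is exposed.** Three of the four discontinuation criteria need no symptom: above 8 x ULN; above 5 x ULN for more than 2 weeks; above 3 x ULN with raised bilirubin or INR. Only the fourth requires one. The substitution sentence could also apply to a subject who meets one of the other three and happens to have symptoms.

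**Step 3. What the laboratory outputs keep.**

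- SAP 11.2 summarises ALT, AST, alkaline phosphatase and total bilirubin. SAP 5.3 takes the maximum liver value when a scheduled visit has more than one.
- SAP 13.2 puts all assessments in listings, and protocol 10.6.4 flags out-of-range values there.
- SAP 4.2 plans counts of clinically significant laboratory changes, and SAP 13.2 mentions potentially clinically significant values. The SAP text gives no liver threshold for either.
- The SAP text defines no output that counts subjects meeting a Table 1 criterion or links their enzyme values to their AE terms. SAP section 1 places table and listing specifications in a separate document, so such an output may exist there.
- SAP 5.2 says local laboratory values were not recorded, while protocol 7.5.1 allows local testing for acute management. An episode tested only locally would not be in the central data.

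**Step 4. Illustrative scale.** SAP section 3 gives 15 subjects. Suppose one hypothetical case were recorded under a symptom term only. Exact (Clopper-Pearson) 95% limits:

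- Hepatic term recorded: 1/15 = 6.7%. Lower limit 1 − 0.975^(1/15) = 0.2%. The upper limit solves (1−p)^15 + 15p(1−p)^14 = 0.025, giving 31.9%.
- Symptom term only: 0/15 = 0%. Upper limit 1 − 0.025^(1/15) = 21.8%.

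**The case against.** The strongest reply is that 11.3.6, read as a whole, does not tell sites to hide liver events. That largely stands, and it rules out several stronger readings.

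- A reader might infer that the hepatic term is always lost. It is not. The first paragraph requires the finding to be reported, a diagnosis replaces the symptom term, and the active-management clause names discontinuation. Section 4.5.1 also calls for evaluation of causes, so a case that triggers Table 1 undiagnosed may later acquire a diagnosis.
- A reader might infer that asymptomatic rises are better recorded than symptomatic ones, so that the more worrying presentation is the less visible. The active-management clause is not limited to asymptomatic findings, so the text does not support that inversion.
- A reader might infer that the liver signal vanishes from the study. The enzyme values remain in summaries and listings, 4.5.1 sends each listed abnormality to the Medical Monitor, and 4.6 has the DMC review laboratory data until its last Phase 3 program meeting.
- A reader might take 0/15 against 1/15 as an error in this trial. No document reports such a case, and protocol 1.6.3 describes enzyme increases in the program as infrequent, generally mild and transient.

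What the reply does not remove is the conflict between the three paragraphs. A permissive clause does not override a directive one, and an undiagnosed case can still reach the AE tables as a symptom only.

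**Conclusion.** The point holds as an inconsistency with a limited consequence. For a symptomatic ALT or AST rise meeting the Table 1 symptom criterion, with no diagnosis and with the active-management option not used, the TEAE and discontinuation tables may show a symptom term and no hepatic term. The effect is on the AE record and on how a discontinuation is described; the laboratory data are not lost.

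The 15-subject figures in the working only illustrate scale, since no case is documented. The conclusion assumes that sites follow the substitution sentence as written and that the separate table and listing specifications contain no output linking Table 1 criteria to AE terms. A stated rule produces the weaker record, and correcting it is cheap, so the sponsor should act even though the exposed set of cases is narrow.

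**What to change.** **Protocol 11.3.6.** For liver tests meeting a Table 1 criterion, change *in lieu of* to *in addition to*, and change *may be considered AEs* to *are recorded as AEs*; where a diagnosis is available, the diagnosis is recorded. This makes the second and third paragraphs agree with the first. The Table 1 stopping criteria are untouched.

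**SAP, for data already collected.** The SAP describes enrolment in the past tense, so the rewording may affect few records and the data check may matter more. Add a listing of subjects whose central liver tests meet each Table 1 laboratory threshold, cross-referenced to their reported AE terms and reason for discontinuation. Where no hepatic term was reported, query the site. Medical Monitor contacts can be used to find episodes tested only locally. The sponsor should not place terms of its own in the TEAE tables, because the AE data rest on what investigators reported.

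**Cost.** Two phrases in one section, one listing for 15 subjects, and any resulting queries. The downside is that one episode may carry two preferred terms, one for the laboratory finding and one for the symptom.

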12. STUDY MONITORING

FibroGen or its designee will perform periodic monitoring visits and site closeout visits following the site prequalification and/or initiation of the study site. The investigator must provide direct access to, and allocate sufficient space and time for, the monitor to inspect subject source records, CRFs, queries, collection of local laboratory normal ranges (if applicable), investigational product accountability records, and regulatory documents in accordance with GCP and the ICH E6 guideline.

The purpose of trial monitoring is to verify the following:

- The rights and well-being of human subjects are protected;
- The reported data are accurate, complete, and verifiable from source documents;
- All data are collected, tracked, and submitted by the site to FibroGen or its designee, including unscheduled and missed assessments;
- The reported data are reconciled across all data sources (e.g., laboratory, safety, clinical databases);
- The conduct of the trial complies with the currently approved protocol/amendment(s), with GCP, and with the applicable regulatory requirement(s).

The investigator must also permit the US FDA or other applicable regulatory authorities to inspect facilities and records pertaining to this study if so requested. The investigator must notify FibroGen immediately if he is notified of an inspection pertaining to this study by the U.S. FDA or other applicable regulatory authorities.

12.1. Data Quality Assurance

The following steps will be taken to ensure that the study is conducted by the study site in compliance with the study protocol, GCP, and other applicable regulatory requirements.

- Investigator meeting and/or investigator site initiation;
- Routine study site monitoring;
- Documented study and system training;
- CRF and query review against source documents;
- Collection of local laboratory normal ranges, if applicable.

12.2. Compliance with Laws and Regulations

This study will be conducted in accordance with the US FDA regulations, the ICH E6 Guideline for GCP, the Declaration of Helsinki, and applicable local, state, and federal laws, as well as other applicable country laws.

12.3. Data Collection and Handling

Source Documents

Source records are original documents, data, and records that are relevant to the clinical trial. The investigator will prepare and maintain adequate and accurate source documents. These documents are designed to record all observations and other pertinent data for each subject enrolled in this clinical trial. Source records must be adequate to reconstruct all data transcribed onto the CRFs and resolved queries.

Data Collection, Handling, and Verification

Authorized site personnel will enter all required data onto paper or electronic CRFs. Data may be entered into a validated, clinical database compliant with 21 Code of Federal Regulations (CFR) Part 11 regulations. The database will be a secured, password-protected system with full audit trail.

FibroGen and/or its designee will review all subject data. Data that appear inconsistent, incomplete, or inaccurate will be queried for site clarification.

Adverse events and concomitant medications will be coded using industry standard dictionaries (e.g., Medical Dictionary for Regulatory Activities [MedDRA] and World Health Organization drug dictionaries).

The investigator is responsible for reviewing, verifying, and approving all subject data, i.e., CRFs and queries prior to study completion.

Quality Compliance

A database audit may be conducted to ensure data quality and integrity.

13. HUMAN SUBJECTS

13.1. Ethical Considerations

The study will be conducted in accordance with US FDA regulations, the ICH E6 Guideline for GCP, the Declaration of Helsinki, any other applicable regulatory requirements, and IRB or IEC requirements.

13.2. Communication with the Institutional Review Board or Independent Ethics Committee

This protocol, the informed consent form (ICF), the IB, and any information to be given to the subject must be submitted to a properly constituted IRB/IEC by the investigator for review; these have to be approved by the IRB/IEC before the study is initiated and before any investigational product is shipped to the investigator. In addition, any subject recruitment materials must be approved by the IRB/IEC before the material is presented to the subject.

The investigator is responsible for obtaining reapproval by the IRB/IEC annually or more frequently in accordance with the regulatory requirements and policies and procedures established by the IRB/IEC. Copies of the investigator's annual report and other required report to the IRB/IEC and copies of the IRB/IEC continuance of approval must be furnished to FibroGen. A copy of the signed form FDA 1572 must also accompany the above approval letter provided to FibroGen.

Investigators are also responsible for promptly informing the IRB/IEC of any protocol changes or amendments, changes to the IB, and other safety-related communications from FibroGen. Written documentation of IRB/IEC approval must be received before the amendment is implemented.

Investigators must also enter the names of the staff that are involved in the study on the Delegation of the Authority form and sign the form (including their responsibilities). This form must be updated when responsibilities of the staff change.

13.3. Informed Consent Form

No study procedure may be implemented prior to obtaining a signed, written ICF from the subject or the subject's legally authorized representative. IRB/IEC review and approval are required for the ICF. The final IRB/IEC approved ICF must be provided to FibroGen for regulatory purposes.

If there are any changes to the ICF during the subject's participation in the study, the revised ICF must receive the written approval of the IRB/IEC before use; current subjects must be re-consented to the revised version of the ICF.

13.4. Subject Confidentiality

Release of research results should preserve the privacy of medical information and must be carried out in accordance with Department of Health and Human Services Standards for Privacy of Individually Identifiable Health information, 45 CFR Parts 160 and 164, and Health Insurance Portability and Accountability Act (HIPAA), if applicable.

Subject medical information obtained as part of this study is confidential and may only be disclosed to third parties as permitted by the Informed Consent and HIPAA Authorization Form or separate authorization to use and disclose personal health information signed by the subject, or unless permitted or required by law. The subject may request in writing that medical information be given to his/her personal physician.

14. INVESTIGATOR REQUIREMENTS

The investigator must be medically qualified to directly supervise the conduct of the trial at his or her site. The investigator will permit trial-related monitoring, audits, IRB/IEC review, and regulatory inspection(s), providing direct access to source data/documents.

14.1. Study Medication Accountability

All study drug required for completion of this study will be provided by FibroGen. The recipient will acknowledge receipt of the drug by returning the appropriate documentation form indicating shipment content and condition. Damaged supplies will be replaced.

The roxadustat investigational product, including partial and empty bottles, must be maintained at the study site until FibroGen or its designee verifies drug accountability and provides instruction for the return of the investigational product to FibroGen's drug distribution depot.

Accurate records of all study drug received, dispensed, returned, and disposed of by the study site according to the Study Reference Manual should be recorded using the Drug Inventory Log.

14.2. Disclosure of Data

Data records generated by this study must be available for inspection upon request by representatives of the FDA or other regulatory agencies, national and local health authorities, FibroGen monitors/representatives and collaborators, auditors, and the IRB/IEC for each study site.

The Principal Investigator or sub-investigator should promptly notify FibroGen of any audits scheduled by any regulatory authorities and promptly forward copies of any audit reports received to the sponsor.

14.3. Retention of Records

The investigator shall retain records required to be maintained under 21 CFR 312.62(c) for a period of 2 years following the date a marketing application is approved for the drug for the indication for which it is being investigated. If no application is to be filed or if the application is not approved for such indication, the investigator shall retain these records until 2 years after the investigation is discontinued and the FDA is notified.

If the investigator moves or retires, he or she should identify in writing, the designee who will be responsible for record keeping. Archived data may be retained on electronic records or similar medium if a back-up exists and a hard copy is obtainable if required. No records will be destroyed without the prior written consent of FibroGen.

